6.2 DOCUMENTATION OF ADVERSE EVENTS

All adverse events will be recorded on a specifically designated case report form (CRF) from the time the participant provides consent until the time the event resolves or until 30 days after the participant completes study treatment. Adverse events may be discovered through observing and questioning the participant or receiving an unsolicited complaint and questioning the participant in an objective manner. All adverse events will be recorded, regardless of their severity or relation to study medication or procedures.

All serious adverse events (SAEs) will be reported on a SAE report form in addition to CRFs. Safety data will be reviewed at least every four months by the Independent Data Monitoring Committee (IDMC). The IDMC has the authority to recommend withdrawal of a study participant or termination of the trial because of safety findings.

All SAEs should be reported to the Research Ethics Committee, where in the opinion of the Chief Investigator, the event was:

- 'related', ie resulted from the administration of any of the research procedures; and
- 'unexpected', ie an event that is not listed in the protocol as an expected occurrence

Reports of related and unexpected SAEs should be submitted within 15 days of the event, using the NRES SAE form for non-IMP studies. The Chief Investigator must also notify the Sponsor of all SAEs.

6.3 GRADING AND ATTRIBUTION OF ADVERSE EVENTS

The study site will grade the severity of adverse events experienced by study participants according to the criteria set forth in the NCI-CTCAE Version 3.0.²² This document provides a common language to describe levels of severity, to analyse and interpret data, and to articulate the clinical significance of all adverse events.

Adverse events will be graded on a scale from 1 to 5 according to the following standards in the NCI-CTCAE manual:

Grade 1 = mild adverse event.

Grade 2 = moderate adverse event.

Grade 3 = severe and undesirable adverse event.

Grade 4 = life-threatening or disabling adverse event.

Grade 5 = death.

All adverse events will be recorded and graded whether they are or are not related to disease progression or treatment. The NCI-CTCAE grades will be the primary source for scoring.

Allergic reactions will be graded according to World Allergy Organisation (WAO) criteria for allergic reactions to immunotherapy, modified for use with food-triggered allergic reactions. These can be used to inform as to the appropriate NTI-CTCAE grade (Table 2).

The relation, or attribution, of an adverse event to study participation will be determined by the investigator and recorded on CRF and/or SAE reporting form. The assignment of the causality should be made by the investigator responsible for the care of the participant using the definitions in the table below (Table 3). If any doubt about the causality exists the investigator will discuss with the Chief Investigator. In the case of discrepant views on causality between the investigator and others, all parties will discuss the case.

 $^{{}^{22}}http://ctep.cancer.gov/protocolDevelopment/electronic_applications/docs/ctcaev3.pdf\\$

Version 2.6, 5 June 2018

Imperial College London

Grade 1	Grade 2	Grade 3	Grade 4	Grade 5
Symptom(s)/sign(s) of Gl and/or 1 organ system present Cutaneous Generalized pruritus, urticaria, flushing, or sensation of heat or warmth or Angioedema (not laryngeal) or Gastrointestinal Abdominal cramps, vomiting, or diarrhoea or Upper respiratory Rhinitis - (eg, sneezing, rhinorrhoea, nasal pruritus and/or nasal congestion) or Throat-clearing (itchy throat) or Cough perceived to originate in the upper airway, not the lung, larynx, or trachea or Conjunctival Erythema, pruritus or tearing Other Nausea, metallic taste, or headache	Symptom(s)/sign(s) of 2 or more (not including GI) organ system present or Lower respiratory Asthma: cough, wheezing, shortness of breath (e.g. fall in PEF or FEV1 < 40%, salbutamol-responsive wheeze) or Other Uterine cramps	Lower respiratory Asthma (e.g. fall in PEF or FEV ₁ >40%, wheeze not responsive to salbutamol) or Laryngeal oedema with or without stridor	Lower or upper respiratory Respiratory failure with or without loss of consciousness or Cardiovascular Hypotension with or without loss of consciousness	Death

Table 2: World Allergy Organisation (WAO) Grading System for allergic reactions (modified for applicability for foodtriggered reactions) adapted from J Allergy Clin Immunol 2010; 125:569-74.

Relationship	Description		
Unrelated	There is no evidence of any causal relationship		
Unlikely	There is little evidence to suggest there is a causal relationship (e.g. the		
	event did not occur within a reasonable time after administration of the		
	trial medication). There is another reasonable explanation for the event		
	(e.g. the participant's clinical condition, other concomitant treatment).		
Possible	There is some evidence to suggest a causal relationship (e.g. because		
	the event occurs within a reasonable time after administration of the		
	trial medication). However, the influence of other factors may have		
	contributed to the event (e.g. the participant's clinical condition, other		
	concomitant treatments).		
Probable	There is evidence to suggest a causal relationship and the influence of		
	other factors is unlikely.		
Definitely	There is clear evidence to suggest a causal relationship and other		
	possible contributing factors can be ruled out.		
Not assessable	There is insufficient or incomplete evidence to make a clinical		
	judgement of the causal relationship.		

 Table 3: Assignment of causality for adverse event

7. STATISTICS AND DATA ANALYSIS

7.1 SAMPLE SIZE ESTIMATION

Current data from Europe and North America indicates that at least 80-85% of peanut-allergic children will react to 1.4g peanut protein. The incidence of natural resolution of peanut allergy over a 12 month period is typically <10%, on the basis of data arising from our clinical service.

For the purpose of this study, we have assumed a conservative estimate of 10% for natural resolution, and a 20% dropout rate. We note that such is the demand for OIT that in the published studies, drop-out rates have been consistently <10%.

We propose to recruit 46 peanut-allergic children to the study, who will be randomized 2:1 to active (n=30) or control (n=16) groups. This will allow us to detect a rate of successful desensitisation of 60% in participants undergoing OIT, with 80% power using a two-sided significance level of 0.05 and with continuity correction, whilst allowing for a 20% loss-to-follow-up.

These figures for desensitisation rate and resolution are based on published data relating to the UK.⁷

7.2 STATISTICAL ANALYSIS PLAN

Data will be collected on paper CRFs which include the patients name, DOB and hospital number. Participants will be assigned a study number, which will be noted on the paper record. Data will then be entered on to a password-protected computer database on the secure hospital IT system; only the study number will be used to identify the patient data.

De-identified data and all appropriate documentation will be stored for a minimum of 10 years after the completion of the study, including the follow-up period.

The primary analysis will be performed on an intention to treat basis: all subjects allocated to each arm will be analysed together as representing that treatment arm, irrespective of compliance and whether or not they have completed the prescribed regimen. A secondary analysis will also be performed on a per protocol basis.

Subjects who are withdrawn from active treatment will remain in the study for assessment of outcome relating to QoL measures.

7.2.1 ANALYSIS OF PRIMARY ENDPOINT

The primary analysis will compare the proportion of subjects who tolerate 1.4g (or more) roasted peanut protein in the active and control groups, 12 months after randomization, using a two-sided Fisher's exact test at a p<0.05 level of significance.

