5.2 DOUBLE-BLIND, PLACEBO-CONTROLLED FOOD CHALLENGE (DBPCFC) TO ROASTED PEANUT

All participants who fulfil eligibility criteria for the study will undergo a baseline DBPCFC to roasted peanut at enrolment. The DBPCFC is established as the gold-standard test of diagnosis of food allergy by international consensus. The objectives are:

- i. to confirm the diagnosis of IgE-mediated peanut allergy,
- ii. to determine the threshold of clinical reactivity to peanut prior to OIT

The DBPCFC involves 2 half-day visits, at least one week apart. Participants are given incremental doses of peanut or placebo 30 minutes apart, and monitored for signs/symptoms of allergic reaction throughout. The challenge is halted once pre-determined stopping criteria have been reached. DBPCFC will be performed according to the international PRACTALL consensus for best practice.¹²

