5.2.2 DBPCFC

The challenge will consist of seven consecutive increasing doses of roasted peanut (or placebo) at 30 minutes intervals with an observation period of 2 hours after the final dose:

Protocol 1: DBPCFC to peanut	Roasted peanut OFC (using defatted flour)			
TIME POINT (mins)	Peanut flour (mg)	Peanut protein (mg)		
0	6	3		
30	20	10		
60	60	30		
90	200	100		
120	600	300		
150	2000	1000		
180	6000	3000		
Cumulative dose 4443mg				
2 hours observation period following last dose to monitor for signs of reaction				

The food challenge doses will be prepared prior to challenge, in a matrix containing soya (soya-allergic children will be given a matrix based on sunflower seed instead). Tolerance to at least one of these will be established at enrolment. All doses (irrespective of active or placebo) will be double-checked prior to administration. The order of challenge days (active or placebo control) will be randomized by an independent research associate, according to a computergenerated randomization list (www.sealedenvelope.com). The randomization key will be recorded in a separate file and logged once both pair of challenges have taken place.

In brief, symptoms will be monitored during the challenge, with detailed assessment prior to each challenge dose, according to Figure 3.

- Green symptoms: Not generally sufficient to consider a challenge positive unless symptoms persist for at least 120 minutes.
- Orange symptoms: Symptoms that recur on 3 doses, or persist (e.g. 40 minutes) are more likely indicative of a reaction than when such symptoms are transient and not reproducible. 3 or more scoring areas in orange more likely represent a true response, and if present the challenge should be halted.
- Red symptoms: A single red symptom is likely to indicate a true response, and if present the challenge should be halted.

The outcome of the challenge (positive or negative) and the apparent eliciting threshold dose will be recorded in the participant record.

Challenge outcome will be determined as per the PRACTALL Consensus criteria,⁹ as shown in Figure 3:

```
I. SKIN
        A. Pruritus
              0 = Absent
              1 = Occasional scratching
              2 = Scratching continuously for >2 minutes at a time
              3 = Hard continuous scratching causing excoriations
        B. Urticaria/Angioedema
              0 = Absent
              1 = < 3 hives, or mild lip oedema

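### The primary test in 7.2.1 uses neither the baseline eliciting dose nor the Ara h 2 stratum: it is valid and adequately powered, but gives up efficiency and interpretability that the trial has already paid for

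*Combined protocol and SAP*

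**What the plan says.** Section 7.2.1 defines a single primary analysis: "The primary analysis will compare the proportion of subjects who tolerate 1.4g (or more) roasted peanut protein in the active and control groups" at 12 months, "using a two-sided Fisher's exact test at a p<0.05 level of significance". It names no covariate, stratum, effect estimate or confidence interval. Section 7.2 adds a per-protocol analysis but no adjusted analysis of the primary endpoint.

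Section 5.2 gives every child a blinded roasted-peanut challenge before randomisation. One of its two stated purposes is "to determine the threshold of clinical reactivity to peanut prior to OIT". Section 5.2.2 describes the ladder: "The challenge will consist of seven consecutive increasing doses of roasted peanut (or placebo) at 30 minutes intervals", that is 3, 10, 30, 100, 300, 1000 and 3000 mg of protein. Exclusion 6 in section 4.2 removes children who already tolerate 1.4 g or more at that challenge.

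Randomisation (5.3.2) is blocked and stratified on Ara h 2 phenotype only. Section 3.2 justifies this as protection against results being skewed by the luck of allocation. In the efficacy analyses, baseline threshold appears only in 7.2.2, in the secondary comparison of relative change in NOAEL and LOAEL.

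**The concern.** The endpoint is a final threshold judged against a fixed cut-off, so the starting threshold sets the distance each child has to travel. Two children who both fail at 12 months may have needed very different gains. If starting threshold predicts passing, a test that ignores it gives up power. In a trial of 46, a chance difference between arms in starting threshold would also leave readers unsure how much of the observed difference in pass rates reflects it. The plan offers no pre-specified analysis that would answer them. The Ara h 2 factor is in a similar position: it was thought important enough to stratify on, and is then left out of the analysis.

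**Working it through.** **Inputs.** Control rate and loss (7.1): "we have assumed a conservative estimate of 10% for natural resolution, and a 20% dropout rate". Active rate (7.1): "detect a rate of successful desensitisation of 60% in participants undergoing OIT". Allocation (7.1): "who will be randomized 2:1 to active (n=30) or control (n=16) groups". Design target (7.1): "with 80% power using a two-sided significance level of 0.05 and with continuity correction". Dose ladder: 5.2.2. Entry limit: 4.2.

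**1. Steps to be gained.** Cumulative doses are 3, 13, 43, 143, 443, 1443 and 4443 mg, so 1.4 g is reached by clearing the 1000 mg step. Children who clear it at baseline are excluded, so eligible eliciting doses are 3, 10, 30, 100, 300 or 1000 mg. A child who reacted at 1000 mg must gain one step, and a child who reacted at 3 mg must gain six.

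**2. The plan's sample size.** With k = 30/16 = 1.875 and pooled rate p = (0.1 + 1.875 × 0.6)/2.875 = 0.426, the control-arm size before continuity correction is

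n = [1.96 √(p(1-p)(1+1/k)) + 0.842 √(0.1×0.9 + 0.6×0.4/k)]² / 0.5² = 10.15.

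With the correction, n' = (n/4)[1 + √(1 + 2(1+1/k)/(0.5n))]² = 13.04. The active arm is 1.875 × 13.04 = 24.45, the total 37.49, and 37.49/0.8 = 46.9 recruited. An exact 2:1 split gives 38.2 and 47.8. The stated 46 is therefore reproduced to within 2.

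**3. Power of the planned test.** After 20% loss the arms are 30 × 0.8 = 24 and 16 × 0.8 = 12.8, or 13. Power is the sum over all tables (x, y) of Bin(x; 24, 0.6) × Bin(y; 13, 0.1) where Fisher's p < 0.05. This gives 0.853 at 24 v 13 and 0.934 at 30 v 16. If the 20% lost count as failures (48% v 8% at 30 v 16), it is 0.82. The target of 80% is met each time. Fisher's true size at a common rate of 0.1 or 0.4 is 0.020-0.035.

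**4. Two-level stratified exact test (100 mg or less v 300 mg or more).** Assumed baseline mix: 20/25/30/25% at ≤30/100/300/1000 mg. Assumed pass rates across those groups:
- strong: active 0.30/0.50/0.70/0.85, control 0/0/0.08/0.30;
- moderate: active 0.45/0.55/0.65/0.75, control 0.03/0.07/0.12/0.18;
- none: 0.60 and 0.10 throughout.

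With 8,000 simulated trials per setting:

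| Prognosis | 24 v 13: Fisher → stratified | 30 v 16: Fisher → stratified |
|---|---|---|
| strong | 86.7 → 90.4% (+3.7) | 93.7 → 96.0% (+2.3) |
| moderate | 86.3 → 87.1% (+0.8) | 93.7 → 93.9% (+0.2) |
| none | 85.4 → 85.2% (-0.2) | 93.1 → 92.0% (-1.1) |

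**5. Ordered baseline dose.** Here the log-odds of passing are linear in the six dose levels, with marginal rates held at 60% and 10%. The adjusted test permutes treatment against residuals adjusted for baseline dose (3,000 trials per cell, 600 permutations). Ranges cover a uniform and a mid-peaked baseline distribution, at 24 v 13:

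| Odds ratio per step | Fisher | Mid-p Fisher | Two-level exact | Permutation |
|---|---|---|---|---|
| 1 | 0.84-0.86 | 0.86-0.88 | 0.84-0.86 | 0.88-0.89 |
| 1.5 | 0.86 | 0.88 | 0.86-0.87 | 0.90-0.91 |
| 2 | 0.85-0.86 | 0.87-0.88 | 0.87-0.89 | 0.92-0.95 |
| 3 | 0.86 | 0.88 | 0.91-0.93 | 0.96-0.97 |

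The permutation test kept its size (0.047-0.054). Its advantage of 2-3 points at odds ratio 1 is only Fisher's conservatism removed. Against mid-p, the gain is 3-4, 5-7 and 7-9 points at odds ratios 1.5, 2 and 3. If the true active rate were 50% (24 v 13, mid-peaked), Fisher has 0.64, mid-p about 0.71-0.72, and the permutation test 0.77 (odds ratio 2) to 0.82 (odds ratio 3). These runs do not include Ara h 2 strata, because the documents do not give the prevalence of that phenotype.

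**6. Chance imbalance.** Under the mix in step 4, 30% + 25% = 55% react at 300 mg or above. The arms differ by more than 20 points in that share in about 23% of trials at 24 v 13 and 18% at 30 v 16. To size the effect, pool the step 4 rates into the two strata. In the strong case the active rates are 0.185/0.45 = 0.41 and 0.4225/0.55 = 0.77 (36 points apart), and the control rates are 0 and 0.099/0.55 = 0.18 (18 points apart). A 20-point imbalance then moves the risk difference by 0.20 × 18 to 0.20 × 36, about 4-7 points. In the moderate case the gaps are 19 and 9.5 points and the shift is about 2-4 points. The planned difference is 50 points.

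**The case against.** The best defence is that nothing is broken. A reader might infer that ignoring baseline threshold biases the primary comparison, or that the p-value cannot separate a treatment effect from baseline imbalance. The documents do not support that. Under randomisation, Fisher's p-value already allows for chance imbalance in every covariate, measured or not, and its true size here is below 5%. A reader might also infer that the trial is underpowered for want of adjustment; step 3 shows that it is not. Both parts of this defence stand.

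The prognostic role of baseline dose is also assumed. The design gives some reason for doubt: the starting step depends on tolerance of boiled peanut (5.3.4), and all children who move to roasted peanut are led towards the same top step (Table 1 in 5.3.4.1). If low-threshold children gain proportionately more steps, the link disappears. This stands as a limit on the size of the gain. It does not make the factor irrelevant, because the fixed cut-off makes some association likely.

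The secondary analysis of relative change in threshold does use baseline dose, so the information is not wholly discarded. It does not adjust the primary comparison, however. Finally, changing the primary test late in an open-label trial has a credibility cost, and a coarse two-level split gains little unless the association is strong. Both points stand and shape the remedy.

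**Conclusion.** The point holds as a cheap improvement. The primary test leaves out a baseline measurement that defines how far each child must move, and also the one factor used to stratify randomisation. The cost is lost efficiency, and no planned way to interpret the result if the arms happen to differ at baseline. Type I error and the planned 80% power are both intact.

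The size rests on assumptions the documents cannot settle. In the pass-rate scenarios, a two-level stratified test changes power by about -1 to +4 points; only the steepest logistic gradient tried, a threefold odds ratio per step, takes that to 5-7 points at 24 v 13. An ordered-dose permutation test gives about 0.90-0.97 against 0.85 at 24 v 13 if baseline is prognostic, with 2-3 points of that due to Fisher's conservatism. A 20-point baseline imbalance would move the estimated difference by a few points against a planned 50, so it would matter mainly for the precision and reading of the estimate, or if the true effect were smaller than planned.

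**What to change.** Before any month-12 outcome data are analysed, amend 7.2.1 to pre-specify a baseline-adjusted primary comparison. A suitable choice is a two-sided permutation test that permutes treatment within Ara h 2 strata and uses baseline eliciting dose as an ordered or log-dose score. Report an adjusted risk difference with 95% CI, and name the method for both. Ordinary logistic regression is a poor basis, because only 13 × 0.10 = 1.3 to 16 × 0.10 = 1.6 control passes are expected and the model may separate; a penalised likelihood avoids this. Keep the unadjusted Fisher test as a sensitivity analysis. If month-12 outcomes have already been analysed, leave Fisher as primary and add the adjusted analysis, labelled as supportive.

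The cost is SAP wording and a slightly more complex analysis, with no extra children, visits or measurements. The downsides are a late change to the primary test in an open-label trial, which the amendment should date and justify, and little or no gain if baseline dose proves not to be prognostic (about 1 point of power lost if the two-level stratified test were used instead).

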7.2.2 ANALYSIS OF SECONDARY ENDPOINTS

The following secondary analyses will be performed, using two-sided testing for non-parametric data at a p<0.05 level of significance:

- Relative change in clinical threshold (NOAEL, LOAEL) to roasted peanut at 6 and 12 months in active vs control, using Mann-Whitney U test.
- Proportion of subjects who tolerate 1.4g (or more) roasted peanut protein in the active and control groups, 12 months after randomization and following cessation of all peanut intake for 4 weeks after 1 and 3 years of OIT, using a two-sided Fisher's exact test at a p<0.05 level of significance.
- Change in quality of life assessments before, and at 6 and 12 months after OIT, as assessed by FAQL-Questionnaire in children, teenagers and their parents in the active vs control groups using paired and group comparisons by non-parametric testing.
- The incidence of adverse events experienced between active and control groups. Statistical differences will be
 determined using Fisher's exact test for proportions or using non-parametric tests for graded reactions.
 Logistic regression will be used to assess the influence of age, gender, asthma status and prior history of
 anaphylaxis on incidence of adverse events.
- Immunological outcome measures pre-, during and post- 12 months of OIT, using Mann-Whitney U test (for paired comparisons) or Friedman's test (for trends over time).

